#### *Quantitative vaginal cultures and quantitative PCR*

Meaningful changes will be defined by greater than or equal to 1 log changes in dominant members of the microbiota, including *Lactobacillus* species, *Gardnerella vaginalis*, key anaerobic microorganisms, *Enterococcus* species, *Escherichia coli*, *Staphylococcus aureus*, Group B *Streptococcus*, and *Candida* species.

#### *Levels of anti-viral activity in CVL*

*In-vitro* anti-HIV activity will be determined by the TZM-bl assay.

The TZM-bl assay will determine HIV-1 infection by luciferase for single round of replication. To assess the potency of the CVL, serial dilutions will be made and tested to determine the IC50.

#### *Levels of cytokine and innate immunity factors*

Changes in cervical cytokine expression and innate immunity factors in cervicovaginal lavage will be assessed. Changes within each group will be reported.

#### Exploratory: Pharmacokinetic (PK)/ Persistence of Eudragit® in CVL

Persistence of polymer will be determined as detected levels of polymer in vaginal fluid collected through cervicovaginal lavage.

### **9.4 Blinding**

All participants will receive a single dose of the vaginal film. They will be randomized to the timing of Visit 3. This will not be blinded.

### **9.5 Random Assignment**

The randomization scheme will be generated and maintained by a member of the Data Management Division at the study site. Women will be randomized to one of the four arms at a 1:1:1:1 ratio using a permuted block design with random block sizes of 4 and 8. In order to minimize bias in group assignment, participants will be given study identification numbers. A study staff member will allot the identification numbers in sequential order as participants become eligible to enroll in the study. These numbers will be randomly assigned with timing of Visit 3. The randomization scheme will be created for a total of 72 participants; the overage will be created to compensate for participant withdrawals or unusable products.

## **9.6 Data Monitoring and Analysis**

### **9.6.1 Data Monitoring**

This clinical trial will be conducted in compliance with the protocol, GCP guidelines, and applicable regulatory requirements. All research charts are maintained in locked files in a locked room. The research staff, under the direction of the primary investigator, will create and maintain an electronic database on the hospital system on the computers in the Reproductive Infectious Diseases research offices. The database will be backed up every night onto the server's back-up system, and weekly onto an external storage device. Appropriate firewall and virus scanning software are installed and updated routinely by the hospital support staff.

This study will utilize electronic data capture. Once the source documents are ready for computer entry, site staff will enter data into a data entry system. Study data management staff will review the electronic data elements for completeness and accuracy. If there are any responses that are incomplete, unclear, or inconsistent with related data elements, the staff person will speak with the clinician in question as soon as possible to resolve the problem. If necessary, the study staff will make the appropriate change in the electronic database which tracks time and date a change is made.

### **9.6.2 Primary Endpoint Analysis**

The number of adverse events will be summarized by severity, body system, and relationship to study product using frequencies, percent, and 95% confidence intervals. Individual participants will contribute once to the calculation of event rates.

### **9.6.3 Secondary and Exploratory Endpoint Analysis**

Summary statistics of frequencies, percentages, and 95% confidence intervals will be provided for categorical data. Means, standard deviations, medians, ranges and 95% confidence

intervals will be provided for continuous data. Methods for the analyses of the secondary endpoints are described below.

One-way analysis of variance (ANOVA) and Kruskal-Wallis tests will be used, where appropriate, to evaluate differences in the following continuous variables between the study arms: levels of glycoproteins and mucins in CVL, levels of cytokines and innate immunity factors, and antiviral activity in CVL. Between groups, pre- to post-exposure changes in the above endpoints will also be evaluated using ANOVA and Kruskal-Wallis tests, where appropriate, while paired Student's t- and Wilcoxon signed-rank tests will be used to evaluate these changes within each study arm. Mixed effects linear regression will be used to evaluate associations between days of exposure to study product and these outcomes.

Nugent score will be categorized as follows: normal (score 0-3), intermediate (score 4-6), and bacterial vaginosis (score 7-10). Differences in the categorized Nugent score pre and post exposure levels will be evaluated using Fisher's exact, while McNemar's tests will be used to evaluate pre- to post-exposure shifts between normal (score 0-3) and abnormal (score 4-10) vaginal microflora within each study arm.

Prevalence of microorganisms at each visit will be compared between the study arms using Fisher's exact tests, while pre- to post-exposure shifts will be evaluated within each group using McNemar's tests. Differences between the study arms in the quantity of microorganisms at each visit, as well as the change in quantity, will be evaluated using Mann-Whitney U tests. Meaningful changes will be defined by greater than or equal to 1 log changes in dominant members of the microflora, including Lactobacillus (H2O2 positive and negative strains), anaerobic gram negative rods, Gardnerella vaginalis, Candida species, facultative gram negative rods, Streptococci and facultative gram positive cocci and rods. Fisher's exact tests will be used to evaluate differences in these changes between study arms. Mixed effects linear regression (for continuous outcomes) and generalized estimating equations (for binary outcomes) will be used to evaluate associations between days of exposure to study product and these outcomes.

Time since last menstrual period will be included as a potential confounder in these analyses.

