### 9.2 Sample Size and Accrual

The primary aim of the study is to assess the local and systemic safety of a single dose of placebo vaginal film. The primary endpoint is the proportion of participants who experience a Grade 2 or higher adverse event. The proposed total sample size is N=64 divided into 4 arms (placebo film with follow up at days 3, 7, 10, or 14 assigned at a 1:1:1:1 ratio). Based on previous studies of vaginal products conducted at the study site, the accrual of 64 eligible subjects with normal reproductive tracts is expected to require the screening of approximately 150 volunteers. Since unevaluable participants will be replaced, it is anticipated that 64 women exposed to study product will complete study visit 3.

The sample size is based on the exact binomial probability of observing at least two Grade 2 or higher Adverse Events. For a given arm, if the true rate of a given toxicity endpoint is 5%, 16 women per arm provide 80% power to exclude toxicity endpoint rates greater than 27% (the probability of observing zero or one event is less than 0.05 when the true rate is 27%).

Table 6: Power Calculations for FAME 101

Event Rate	P(No events   n=16)	P(1 or more events   n=16)	P(2 or more events   n=16)
1%	0.851	0.149	0.011
5%	0.440	0.560	0.189
10%	0.185	0.815	0.485
15%	0.074	0.926	0.716
20%	0.028	0.972	0.859
25%	0.010	0.990	0.937
27%	0.007	0.993	0.955
30%	0.003	0.997	0.974
35%	0.001	0.999	0.990

In previous studies of two different placebo film products the combined frequency of Grade 2 or higher Adverse Events was 19%. Assuming a similar frequency in the current study, a sample size of 64 women will assure that a 95% confidence interval for the Grade 2 or higher Adverse Events rate has an upper limit of no greater than 30%.

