#### Exploratory: Vaginal Microenvironment

Given that there is no non-product use arm, participants will serve as their own control. Assessment of baseline microenvironment will take place during the enrollment visit with the exception of CVL properties. CVL will be obtained at the screening visit so that the microenvironment can recover prior to study product administration at the enrollment visit.

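### Between-arm tests on the exploratory CVL endpoints leave out the Visit 1 value already collected; adding it as a covariate is a nearly free gain in precision

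*Combined protocol and SAP*

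**What the plan says.** For glycoproteins and mucins, cytokines and innate immunity factors, and antiviral activity in CVL, Section 9.6.3 plans one-way ANOVA or Kruskal-Wallis between arms on the levels. It then adds a second comparison: "Between groups, pre- to post-exposure changes in the above endpoints will also be evaluated using ANOVA and Kruskal-Wallis tests". Changes within each arm get paired t or signed-rank tests.

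The same section plans a regression for the same outcomes: "Mixed effects linear regression will be used to evaluate associations between days of exposure to study product and these outcomes". It does not say whether, or how, the baseline visit enters. The only covariate named is in the closing sentence of the section: "Time since last menstrual period will be included as a potential confounder in these analyses".

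A baseline exists for each of these endpoints. Table 2 and Appendix 1 list the CVL assays at Visit 1, and Section 9.3.2 gives the reason for that timing: "CVL will be obtained at the screening visit so that the microenvironment can recover prior to study product administration". Section 7.2 allows screening up to 45 days before enrollment. Section 9.2 sets out the design as "placebo film with follow up at days 3, 7, 10, or 14 assigned at a 1:1:1:1 ratio", 64 women in all, and replaces unevaluable women, so 16 per arm are expected at Visit 3.

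**The concern.** Arms are randomised and the Visit 1 CVL value precedes randomisation, so it can be used as a covariate without risk of bias. The plan uses it in one between-arm test by subtracting it (in effect fixing its slope at 1) and ignores it in the other (slope fixed at 0). Subtraction helps only when the baseline predicts follow-up well. With a common SD, a change score is noisier than the follow-up value alone whenever rho is below 0.5.

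A modest rho is plausible here. The baseline lavage can precede the film by 45 days, and Visit 3 can fall as late as day 16 (Section 7.4), so the two samples may be up to 45 + 16 = 61 days apart and at different points of the cycle. The documents report no correlation, so this remains a possibility only.

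At stake is the chance of seeing an effect of wear time on mucins, cytokines or antiviral activity in a trial sized on adverse events alone. With two tests per endpoint and no stated priority, the plan also leaves open which result carries the between-arm conclusion.

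**Working it through.** **The plan's own figure.** Section 9.2 gives 80% power with 16 per arm to exclude a toxicity rate above 27% when the true rate is 5%. The exact binomial agrees: P(0 or 1 event | n=16, 5%) = 0.811 and P(0 or 1 | n=16, 27%) = 0.045. That calculation concerns adverse events. The plan states no power, SD, effect size, correlation or alpha for the CVL comparisons, so everything below rests on assumptions.

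**Inputs.** From the plan: 4 arms of 16, N = 64. Assumed: equal SD (set to 1) at Visit 1 and Visit 3; rho of 0.3, 0.5 or 0.7; two-sided alpha 0.05; arm means of 0, 0.3, 0.6 and 0.9 SD.

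**Residual variances.**
- Follow-up value only: 1
- Change score: 2(1 − rho)
- Baseline-adjusted (ANCOVA): (1 − rho²) × [1 + 1/(64 − 4 − 2)] = (1 − rho²) × 1.017, where the factor charges for estimating the slope

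**Noncentrality.** The mean of the arm means is 0.45, and the squared deviations sum to 0.2025 + 0.0225 + 0.0225 + 0.2025 = 0.45. So lambda = 16 × 0.45 / variance = 7.2 / variance. The F test has 3 and 60 degrees of freedom, or 3 and 59 for ANCOVA.

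| rho | Variance: value / change / ANCOVA | lambda: value / change / ANCOVA | Power: value / change / ANCOVA |
|---|---|---|---|
| 0.3 | 1 / 1.40 / 0.926 | 7.20 / 5.14 / 7.78 | 57% / 43% / 61% |
| 0.5 | 1 / 1.00 / 0.763 | 7.20 / 7.20 / 9.44 | 57% / 57% / 70% |
| 0.7 | 1 / 0.60 / 0.519 | 7.20 / 12.00 / 13.88 | 57% / 81% / 87% |

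**Gain over the better planned test.** The ratio of the ANCOVA variance to the smaller of the two planned variances is 0.93 at rho 0.3, 0.76 at 0.5, 0.519/0.60 = 0.86 at 0.7, 0.97 at 0.9 and about 1.00 at 0.97. At rho 0 it is 1.017, so the worst case is a loss of under 2% in variance. In women per arm, the better planned test would need 16/0.926 = 17.3, 16/0.763 = 21.0 and 18.5 at rho 0.3, 0.5 and 0.7 to match ANCOVA with 16.

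**A different effect shape.** In a simulation (4,000 runs per setting) with one arm shifted by an assumed 1 SD, overall F-test power for value / change / ANCOVA was 82% / 66% / 86% at rho 0.3, 81% / 82% / 91% at 0.5, and 81% / 96% / 98% at 0.7. With no effect, the change-score and ANCOVA tests rejected in 4.4% to 5.3% of runs, so both hold their level.

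**The days-of-exposure regression.** As a stand-in, take a one-degree-of-freedom linear trend on days 3, 7, 10 and 14 with the same arm means. Without baseline its power on the follow-up value is 75% at every rho; on the change score it is 75% at rho 0.5 and 93% at 0.7. With the baseline value as covariate it is about 79%, 86% and 96% at rho 0.3, 0.5 and 0.7. Charging for the slope takes off less than one point.

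**The case against.** The strongest reply is that the planned regression already answers the question. All women receive the same film, arms differ only in the day of Visit 3, and Section 2.3 says visible film comes out with the Visit 3 lavage, so the arm essentially sets days of exposure. An effect of wear time is exactly what that regression estimates. For a linear gradient, its unadjusted trend (75% at rho 0.3 and 0.5) beats even the adjusted overall F test (61% and 70%). If the baseline visit enters at zero days with a common mean across arms, baseline is already used.

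Much of this stands. A reader might infer that the plan has no analysis able to use baseline, or that the regression is beside the point; neither follows from the text. What survives is that Section 9.6.3 does not say how baseline enters, and that adding it improves the trend test as well (75% to 86% at rho 0.5).

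A reader might also take the gain at rho 0.3 to be 43% to 61%. That compares adjustment only with the weaker planned test. The test on values already reaches 57%, so the fair gain is 57% to 61%.

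Finally, the stakes are modest. The objective is a pre-to-post comparison with each woman as her own control, which the paired tests address, and Table 7 lists only descriptive statistics and intervals for these endpoints. That is correct, and it limits the weight of the point.

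**Conclusion.** The point holds as a free improvement on exploratory CVL endpoints. Neither between-arm ANOVA conditions on a baseline the trial already collects, and conditioning on it is at least about as precise as the better of the two at ordinary correlations. For the assumed gradient, the gain in F-test power over that better test is about 4, 13 and 6 points at rho 0.3, 0.5 and 0.7. It is negligible near rho 0.9 or above, and also near zero correlation, where the value-only test is just as good.

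These sizes depend on the assumed rho, equal SDs, effect shape and alpha. The direction does not, apart from a loss of under 2% in variance at the extremes. The variance argument applies to the ANOVA; for Kruskal-Wallis it carries over only by analogy to a rank-based version.

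A reader might go further and call the change-score tests biased or invalid, or the safety conclusion weakened. The documents support neither: under randomisation both tests hold their level, and the adverse-event endpoint and N=64 do not depend on them.

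**What to change.** In Section 9.6.3:

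- Make the between-arm comparison for each CVL endpoint a linear model of the Visit 3 value (log scale where skewed) on randomised arm, with the Visit 1 value on the same scale as covariate. Use a rank-based version where Kruskal-Wallis was planned.
- State that the days-of-exposure regression includes the Visit 1 value, either as a covariate or as a zero-exposure visit with a common mean across arms.
- Keep the within-arm paired tests as they are. Keep the unadjusted value and change-score comparisons as descriptive support, and say that the adjusted model carries the between-arm conclusion.

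The cost is one degree of freedom per model and a few lines of SAP text. It needs no new sample, visit or participant.

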### **3.3 Exploratory Objectives**

- **Vaginal Microenvironment**

- To compare the effects of the placebo film on the vaginal microbiota and glycome pre and post study product use.

- **Persistence**

- To describe the persistence of the placebo vaginal film at 3, 7, 10 and 14 days after insertion

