#### *Nugent Score*

Clinically significant changes in vaginal flora will be evaluated by a change in the Nugent score baseline (Visit 2, pre-exposure) to Visit 5. The Nugent score is graded 1 to 10 as follows:

Normal, 0 to 3

Intermediate, 4 to 6

BV, 7-10

Any shift from normal at baseline to intermediate or BV at Visit 3 or 4, or shift from intermediate or BV to normal at Visit 3 or 4 will be considered a scientifically meaningful change in vaginal microbiota.

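### Section 9.6.3 places every paired pre/post test with a stated grouping inside one arm of about 16 women and expressly names no within-woman change averaged over all 64.

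*Combined protocol and SAP*

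**What the plan says.** Section 3.3 gives the aim: "To compare the effects of the placebo film on the vaginal microbiota and glycome pre and post study product use". Section 9.4 states that "All participants will receive a single dose of the vaginal film"; the arms differ only in when Visit 3 falls (day 3, 7, 10 or 14). Section 9.3.2 adds: "Given that there is no non-product use arm, participants will serve as their own control".

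Section 9.6.3, with related entries elsewhere, then provides:

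- **CVL markers (glycoproteins and mucins, cytokines and innate factors, antiviral activity).** Paired t and "Wilcoxon signed-rank tests will be used to evaluate these changes within each study arm". ANOVA and Kruskal-Wallis compare the changes between arms. For cytokines, section 9.3.2 also says "Changes within each group will be reported".
- **Nugent score.** McNemar tests for "shifts between normal (score 0-3) and abnormal (score 4-10) vaginal microflora within each study arm". A Fisher test of categorized pre and post levels has no stated grouping. The endpoint definition in 9.3.2, "Any shift from normal at baseline to intermediate or BV at Visit 3 or 4" (and the reverse), mentions no arm.
- **Organism prevalence.** McNemar within each group.
- **Organism quantity.** Mann-Whitney tests between arms, and no paired test.
- **Lectin microarray.** No test is named in 9.6.3. Table 7 lists descriptive statistics with a 95% CI.
- **All-arm models.** A mixed model, or GEE for binary outcomes, relates outcomes to days of exposure. The plan does not say whether the pre-film record enters, or how it and Visit 4 are coded.

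Table 7 lists summaries with 95% CIs and states no grouping.

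**The concern.** The design supplies 64 before-and-after pairs on one product, but the paired tests that state a grouping use them in four sets of 16. Each set answers the before/after question at one follow-up time, with a wide interval. The analyses that do use all arms answer another question: whether the outcome changes per day of exposure. A film that shifts a marker by the same amount at every visit time has no trend across Visit 3 days, yet it has a clear pre-to-post change.

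At stake is how precisely the trial can describe the film's average effect on the microenvironment, and whether that number is fixed before the data are seen. The primary safety analysis is not affected.

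**Working it through.** **The plan's own figure.** The only power statement (section 9.2) concerns adverse events. It reproduces: with n = 16, P(0 or 1 event) is 0.811 at a 5% rate (stated as 80% power) and 0.045 at 27% (stated as below 0.05). No precision or power is given for the paired tests.

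**Inputs.** From the documents: N = 64 in four equal arms, so 64/4 = 16 per arm; Visit 3 at days 3, 7, 10 and 14. Assumed, because the documents give none: two-sided 5%, the effect sizes, the shift rates, and a within-woman correlation of 0.3 to 0.6. SD means the SD of the within-woman change.

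**Precision of a paired mean change.** Half-width = t(0.975, n−1)/√n.

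- One arm: 2.131/√16 = 0.53 SD.
- Pooled: 1.998/√64 = 0.25 SD.

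**Detectable change at 80% power** (noncentral t with noncentrality d√n): 0.75 SD for n = 16 and 0.36 SD for n = 64.

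**Exact McNemar power**, summed over the number of discordant pairs, with 5% improving:

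| Worsening | n = 16 | n = 64 |
|---|---|---|
| 15% | 1% | 33% |
| 20% | 5% | 62% |
| 25% | 11% | 83% |

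In one arm, p ≤ 0.05 needs at least six discordant women all moving the same way (2 × 0.5⁶ = 0.031; five give 0.0625).

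**Against the plan's days model.** This is the fairer comparison. The model is outcome = intercept + woman effect + slope × days, fitted by generalized least squares with known variance, with the pre-film record as day 0 and Visit 3 as the only later record. The pooled test is the paired change averaged over the four arms.

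| Assumed change at days 3/7/10/14 (SD) | Paired test in one arm | Pooled | Days slope |
|---|---|---|---|
| 0.4/0.4/0.4/0.4 | 32% | 88–89% | 79–81% |
| 0.15/0.35/0.45/0.65 (mean 0.4) | – | 88–89% | 95–96% |
| 0.8/0.4/0/0 | 85% (day 3) | 66–67% | 8–13% |
| 0.8/0/0/0 | 85% (day 3) | 35% | – |

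**Entering Visit 4 (flat 0.4 SD).** If the shift persists, the slope has 82% to 90% power: 87–90% if days stop counting at Visit 3, and 82–83% if Visit 4 is day 21. If the effect is gone by Visit 4, power is 7% to 37%, lowest with day-21 coding.

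**What the slope estimates.** For the flat 0.4 SD shift with the pre-film record at day 0 (Visit 4 not entered), the slope is 0.035 to 0.037 SD per day. That implies about 0.11 SD at day 3 (0.037 × 3) and 0.49 to 0.52 SD at day 14 (× 14). It can detect that something changed while misstating the size at both ends.

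**Coding of a pre/post term.** Mean Visit 3 day = (3 + 7 + 10 + 14)/4 = 8.5. With a pre/post term plus days − 8.5, power for the flat shift is 89% if the centred days are set to 0 before film. It is 32% to 37% if the pre-film record is left at −8.5.

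**The case against.** The best defence is that the objective does not ask for a single pooled number. The arms have different exposure lengths and visible film is removed at Visit 3 (section 2.3), so within-arm changes plus a days-of-exposure model suit the design. Pooled routes may also already exist: the mixed model and GEE use all arms, and Table 7 and the Nugent Fisher test state no arm split. Much of this stands. Section 3.3 says before versus after, not over all women, so the pooled change is one sensible reading of the objective and not a requirement. A reader might also infer that the plan rules out pooled analysis. It does not; it only fails to name one. For cytokines, however, the text points to within-group reporting, and the Fisher test treats before and after values as independent.

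A second tempting inference is that pooling always beats the plan. It does not. The days slope wins for a growing effect, and the day-3 arm wins for an effect confined to day 3 or fading after it. If Visit 4 is entered and a flat shift persists, the slope roughly matches the pooled test.

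A third is that the days model has only 5% power with Visit 3 records alone. Under a flat shift the true Visit 3 slope is zero, so 5% is the type I error rate and not a fair comparator. One record per woman would also fit the named repeated-measures methods poorly.

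Finally, the change is uncontrolled, so a narrower interval is not a less biased one. That stands in full.

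**Conclusion.** The point holds in a limited form. Every paired test with a stated grouping is within an arm of about 16, organism quantity has no paired test, and the all-arm models estimate a slope that is not the average pre-to-post change. Naming the pooled change would roughly halve the interval (0.25 against 0.53 SD) and the detectable change (0.36 against 0.75 SD) relative to one arm.

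The gain over the plan's days model is not fixed. It ranges from a clear benefit (fading effects, or a flat Visit 3 effect gone by Visit 4) through little or none (a flat effect that persists, with Visit 4 entered) to a loss (growing effects). The documents do not indicate which shape to expect, and all effect sizes, shift rates and correlations here are assumptions. The documents do not support a claim that the plan fails its objective. No stated figure is wrong, the endpoints are exploratory, and the priority is low: an optional, cheap improvement.

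**What to change.** In section 9.6.3, keep the within-arm tests and the days-of-exposure models, and add:

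1. The within-woman change from the pre-film record (Visit 1 for CVL measures, Visit 2 for swabs) to Visit 3 over all women, averaged over the four arms, with a 95% CI. Cover CVL markers, lectin microarray, organism quantity and prevalence, and Nugent normal versus 4–10.
2. Visit 4 as a separate contrast, because visible film is removed at Visit 3.
3. Explicit coding of the pre-film record in the models: a pre/post term plus centred days (days − 8.5) set to 0 before film, keeping the planned adjustment for time since last menstrual period. State how Visit 4 is coded.
4. A statement of whether the Table 7 changes and the Nugent Fisher test are pooled or by arm.

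The cost is a few sentences and some extra outputs, with no new data. The downside is that the pooled figure averages over exposure lengths and dilutes an early or fading effect, so it must be read beside the arm-level and days results. It remains an uncontrolled change. Baseline CVL is taken at screening, up to 45 days before enrollment (section 7.2), for the reason given in 9.3.2: "CVL will be obtained at the screening visit so that the microenvironment can recover prior to study product administration at the enrollment visit". Enrollment is timed to avoid menses for 14 days, so cycle phase may differ between the records, and pooling does not remove that bias.

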**Table 7: Statistical Analysis Plan**

Endpoint	Variable	Statistics
Primary	Adverse Events	Frequency, Percent, 95% Confidence Interval
Exploratory	Persistence of Eudragit® in CVL	Frequency, Percent, 95% Confidence Interval
	Levels of glycoproteins and mucins, in CVL	Mean, SD, Median, Range, 95% Confidence Interval
	Antiviral activity in CVL	Mean, SD, Median, Range, 95% Confidence Interval

	Change in vaginal flora (Nugent score)	Frequency, Percent, 95% Confidence Interval
	Culture/qPCR results from vaginal organisms	Frequency, Percent, 95% Confidence Interval
	Change in cytokine and innate immunity factors	Mean, SD, Median, Range, 95% Confidence Interval
	Lectin Microarray to assess changes in glycome	Mean, SD, Median, Range, 95% Confidence Interval

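### The Nugent analysis sentence gives Fisher's exact test to a pre/post contrast without naming the groups compared, and no paired test is named for three-category change or for all 64 women pooled

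*Combined protocol and SAP*

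**What the plan says.** Section 9.6.3 deals with the Nugent score in one two-part sentence. It has just defined three categories: normal 0-3, intermediate 4-6 and BV 7-10.

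- First part: "Differences in the categorized Nugent score pre and post exposure levels will be evaluated using Fisher's exact" test. No arms or other groups are mentioned.
- Second part: "McNemar's tests will be used to evaluate pre- to post-exposure shifts between normal (score 0-3) and abnormal (score 4-10"), within each study arm.

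Other parts of the plan bear on how to read it:

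- Section 9.3.2, on the vaginal microenvironment: "Given that there is no non-product use arm, participants will serve as their own control".
- Section 9.3.2, Nugent Score, defines a meaningful change: "Any shift from normal at baseline to intermediate or BV at Visit 3 or 4", or the reverse move to normal.
- Section 9.6.3, on microorganisms, uses the same two-part form but states both contrasts. For Fisher it reads: "Prevalence of microorganisms at each visit will be compared between the study arms using Fisher's exact tests". McNemar's test is kept there for the paired change inside each arm.
- Section 9.2: "The proposed total sample size is N=64 divided into 4 arms", allocated equally, so 16 per arm.
- Table 7 lists the Nugent change as exploratory, with frequency, percent and 95% confidence interval only.

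**The concern.** Fisher's exact test compares proportions in separate sets of people. The only contrast the first part of the sentence names is before versus after, and by design those are the same women. Setting the two visits out as independent rows treats stable differences between women as noise. The test is then conservative and can report no change when flora has shifted.

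There is a second way to run it wrongly. Fisher could be applied to the cross-table of pre category by post category. That tests whether the two are associated, not whether anything changed.

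If the authors meant a comparison between arms, the test is suitable but the sentence does not say so. In either case an analyst must choose a reading, possibly after seeing the data. McNemar's test fills part of the gap, but only for the two-category score and only inside arms of 16.

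**Working it through.** **Setting the sentences side by side.**

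| Outcome (section 9.6.3) | Independent-samples test | Paired test |
|---|---|---|
| Continuous CVL measures | ANOVA / Kruskal-Wallis, between arms | t / signed-rank, within arm |
| Nugent score | Fisher, contrast given as pre and post | McNemar, normal/abnormal, within arm |
| Microorganism prevalence | Fisher, between arms at each visit | McNemar, within arm |

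Only the Nugent row lacks a stated between-arm contrast.

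**What McNemar leaves out.** It uses only women who cross the line between 0-3 and 4-10. A woman moving from intermediate to BV is abnormal at both visits and contributes nothing. As specified, it is also never run on all 64 women.

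**Size on the literal reading.** The documents give no power figure, baseline share or transition rate for Nugent, so these are assumptions. Symptomatic BV is excluded at enrollment (section 5.5) but abnormal flora without symptoms is not, so the baseline abnormal share need not be zero.

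Take 30% abnormal at baseline, 20% of normal women worsening and 10% of abnormal women recovering:

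- normal to abnormal: 0.70 × 0.20 = 0.14
- abnormal to normal: 0.30 × 0.10 = 0.03
- abnormal at both visits: 0.30 × 0.90 = 0.27
- abnormal after exposure: 0.14 + 0.27 = 0.41, a rise of 0.11

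Variance of the change, times n:

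- treated as independent: 0.30 × 0.70 + 0.41 × 0.59 = 0.452
- paired: (0.14 + 0.03) − 0.11² = 0.158

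The unpaired variance is 0.452 / 0.158 = 2.9 times too large.

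Exact enumeration of the paired table, two-sided 0.05, with 10% of abnormal women recovering throughout:

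| Abnormal at baseline | Normal women worsening | n=64: Fisher / exact McNemar | n=16: Fisher / exact McNemar |
|---|---|---|---|
| 20% | 20% | 0.276 / 0.726 | 0.016 / 0.025 |
| 30% | 20% | 0.083 / 0.476 | 0.004 / 0.012 |
| 40% | 20% | 0.017 / 0.249 | 0.001 / 0.005 |
| 30% | 30% | 0.483 / 0.839 | 0.031 / 0.071 |
| 20% | 40% | 0.977 / 0.997 | 0.229 / 0.330 |

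The rates are conditional on baseline state. If 20% and 10% are read as shares of all women, with 30% abnormal at baseline, the n=64 figures become 0.120 and 0.236.

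**Why arms of 16 are weak under either test.** Exact McNemar needs six one-way shifts: 2 × 0.5⁶ = 0.031, against 2 × 0.5⁵ = 0.063 for five. In the 30%/20% case an arm of 16 expects 16 × 0.14 = 2.2 worsening and 16 × 0.03 = 0.5 recovering. Fisher needs 5 to 7 one-way shifts at n=16 as baseline abnormality runs from 0 to 50%. At n=64 it needs 6 to 13, against 6 for McNemar.

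**Worked example, n=64.** Sixteen women are abnormal before; 12 worsen and 2 improve, so 16 + 12 − 2 = 26 are abnormal after.

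- Fisher on 16/64 versus 26/64: p = 0.090
- Exact McNemar: 2 × (1 + 14 + 91) / 2¹⁴ = 212 / 16,384 = 0.013

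**The cross-table misuse.** With 11 women normal at both visits, 5 abnormal at both and no shifts at all, Fisher gives p = 1 / C(16,5) = 1 / 4,368 = 0.0002. That would look like a strong effect when nothing changed.

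**The case against.** The strongest reply is that the plan keeps the pairing where it matters. The second half of the sentence gives McNemar's test to normal/abnormal shifts within each arm, and that is the split section 9.3.2 calls meaningful. The two neighbouring paragraphs follow one pattern, an independent-samples test between arms and a paired test within them. An omitted phrase about study arms is therefore the likeliest explanation. The power comparison also collapses the score to two categories, for which McNemar is already planned, and pools 64 women where the planned paired analysis uses 16. The endpoint is exploratory, and no sample-size claim depends on it.

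Most of this stands. A reader might infer that the plan as a whole discards the pairing, or that it would miss most real flora shifts. The documents support neither. The loss from Fisher depends on the scenario: it is small for large shifts (0.977 against 0.997), and within an arm low power comes mainly from the arm size.

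What remains is narrower. On the likelier reading the sentence still omits its comparison groups. On either reading no paired test is named for the three categories. Nor is one named for all women together. The generalized estimating equations for binary outcomes appear in the microorganism paragraph and concern days of exposure. If they were meant to include normal/abnormal Nugent status they would respect the pairing in a pooled analysis, but the text does not say so, and the three-category gap would remain.

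**Conclusion.** The point holds as a minor defect in the specification of an exploratory analysis. Taken literally, the Fisher clause uses an invalid test for paired data; taken as a between-arm comparison, it states the wrong contrast. McNemar's test is valid for its stated purpose. The missing pieces are a paired test for three-category change and a paired test pooled over arms. The three-category gap lies outside the shift that section 9.3.2 defines as meaningful, which also limits its weight.

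The loss of about 8% against 48% power applies only to the literal reading, 64 pooled women, the normal/abnormal split and the assumed conditional rates. It would be nil or slight with almost no baseline abnormality or with very large shifts. No power figure was worked out for the three-category comparison itself.

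**What to change.** Replace the sentence in section 9.6.3 with text such as:

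> Categorized Nugent score will be compared between the study arms at each visit (Visits 2, 3 and 4) using Fisher's exact test. Pre- to post-exposure change (Visit 2 to Visit 3, and Visit 2 to Visit 4) will be evaluated with paired tests: exact McNemar for normal versus abnormal, within each arm and pooled over arms, and Stuart-Maxwell (marginal homogeneity) for the three categories, pooled over arms.

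The visits should be named because Gram stains are taken at Visits 2, 3 and 4 and section 9.3.2 counts shifts at Visit 3 or 4. That subsection also refers to a Visit 5, which is not in the schedule. A pooled Visit 2 to Visit 3 result averages over 3 to 14 days since insertion and should be reported as such. The Visit 2 comparison between arms describes baseline balance only.

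The cost is a short rewrite of one sentence. No extra participants, visits or specimens are needed.
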